13.5.3 Secondary Analyses

If both primary endpoints are met, then four secondary superiority tests will be evaluated. The secondary hypotheses will be tested in two sequential families, with simultaneous testing of the hypotheses in the second family.

1. Family 1: Secondary Effectiveness Hypotheses
 - a. ECD loss superiority test
2. Family 2: Secondary Safety Hypotheses
 - a. IOP spike rate superiority test
 - b. Mean change from baseline in IOP at 6 hours post-op superiority test
 - c. Mean change from baseline in IOP at 24 hours post-op superiority test

The null hypotheses in Family 2 above will be eligible for rejection only if the primary endpoints and the Family 1 secondary endpoint are met. The overall type I error for the secondary endpoint hypothesis tests in Family 2 above will be controlled by application of the Holm stepwise procedure as follows.

1. The smallest of the three raw p-values will be compared to 0.008333 or, equivalently, tripled and compared to 0.025. If the raw p-value is less than or equal to 0.008333, then the associated null hypothesis will be rejected. Equivalently, if three times the raw p-value is less than or equal to 0.025 then the associated null hypothesis will be rejected.
2. The second smallest of the three raw p-values will be compared to 0.0125 or, equivalently, doubled and compared to 0.025. If the raw p-value is less than or equal to 0.0125, then the associated null hypothesis will be rejected. Equivalently, if two times the raw p-value is less than or equal to 0.025 then the associated null hypothesis will be rejected.

3. The largest of the three raw p-values will be compared to 0.025. If the p-value is less than or equal to 0.025 then the associated null hypothesis will be rejected.

The null hypotheses will be rejected (or not rejected) based on the p-values and the Holm stepwise adjustment and not based on the confidence intervals described below.

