13.2.2 Secondary Hypotheses

The secondary null hypotheses will be eligible for rejection only if both of the primary endpoints are met. As recommended in ICH E9, the nominal alpha risk will be 0.025 for the one-sided secondary superiority hypothesis tests.

The secondary hypotheses will be tested in two sequential families, with simultaneous testing of the hypotheses in the second family.

1. Family 1: Secondary Effectiveness Hypotheses
 - a. ECD loss superiority test
2. Family 2: Secondary Safety Hypotheses
 - a. IOP spike rate superiority test
 - b. Mean change from baseline in IOP at 6 hours post-op superiority test
 - c. Mean change from baseline in IOP at 24 hours post-op superiority test

The overall type I error for the secondary endpoint hypothesis tests in Family 2 above will be controlled by application of the Holm stepwise procedure.

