13.3.4 Detectable Effect Sizes for the Secondary Hypothesis Tests

The secondary effectiveness hypothesis will be tested only if both primary endpoint statistical tests are successful. If the primary endpoints are met and the secondary effectiveness hypothesis is met, then the type I error rate for the three secondary safety hypothesis tests will be controlled using the Holm stepwise procedure. Under this procedure, the smallest of the three raw p-values will be compared to 0.025/3 or, equivalently, tripled

and compared to 0.025. Consequently, detectable effect sizes for one-sided tests with 80% power are presented based on an alpha risk of 0.008.

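### Section 13.5.3 names Holm for the three IOP superiority tests but lists the steps without Holm's stop rule, so read literally they can add claims that Holm would not allow

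*Combined protocol and SAP*

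**What the plan says.** Section 13.2.2 sets the level: "the nominal alpha risk will be 0.025 for the one-sided secondary superiority hypothesis tests". Section 13.3.4 adds that "the type I error rate for the three secondary safety hypothesis tests will be controlled using the Holm stepwise procedure". The three tests are IOP spike rate, mean IOP change at 6 hours and mean IOP change at 24 hours. Section 13.5.3 says that type I error in this family "will be controlled by application of the Holm stepwise procedure as follows", and lists three steps:

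- Step 1: "The smallest of the three raw p-values will be compared to 0.008333"
- Step 2: "The second smallest of the three raw p-values will be compared to 0.0125"
- Step 3: "The largest of the three raw p-values will be compared to 0.025"

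Each step then rejects its null if its own p-value is at or below its own threshold. Steps 1 and 2 also give an equivalent form, in which the p-value is tripled or doubled and compared with 0.025. Neither step 2 nor step 3 mentions the outcome of the step before. The section ends by saying that decisions rest on the p-values and the Holm adjustment rather than on confidence intervals.

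Sections 13.2.2, 13.3.4 and 13.7.3 name Holm without stating a stop rule, and Section 13.3.4 describes only the smallest p-value. The only written condition lies between families: the Family 2 nulls are "eligible for rejection only if the primary endpoints and the Family 1 secondary endpoint are met". Within Family 2 the plan says only that it proceeds "with simultaneous testing of the hypotheses in the second family".

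**The concern.** Holm is a step-down method. The second p-value is examined only if the first null was rejected, and the third only if the second was. The listed steps omit that condition, so a programmer who codes them as written obtains a different rule from the one named.

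The discrepancy runs in one direction. Every Holm rejection also meets the listed thresholds, so the literal steps can only add rejections. Sections 13.5.3.1.1 and 13.5.3.1.2 turn each rejection into a superiority claim for the test OVD. The literal steps can also give an incoherent result, in which a hypothesis with a larger p-value is rejected and one with a smaller p-value is retained. If this came to light after unmasking, two analysts could defend different sets of claims from the same text.

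**Working it through.** **1. The plan's own figures.** With one-sided alpha 0.025 (Section 13.2.2) and three hypotheses, Holm's thresholds are 0.025/3 = 0.008333, 0.025/2 = 0.0125 and 0.025/1 = 0.025. All three match Section 13.5.3. The supporting power figures in Section 13.3.4.1 also reproduce at one-sided 0.008 with 165 per arm: 0.801 for spike rates of 0.117 against 0.256, and 0.800 for a mean difference of 1.797 mmHg with SD 5.0, against 80% stated.

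**2. A case worked by hand.** Take p = 0.010, 0.012, 0.30.

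| Step | Comparison | As listed | Holm |
|---|---|---|---|
| 1 | 0.010 > 0.008333 | retain | retain, stop |
| 2 | 0.012 ≤ 0.0125 | reject | retain |
| 3 | 0.30 > 0.025 | retain | retain |

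The multiplied form has the same defect: 3 × 0.010 = 0.030 and 2 × 0.012 = 0.024, so the smaller raw p-value receives the larger adjusted value. Similarly, p = 0.001, 0.020, 0.024 rejects the first and third hypotheses as listed, but only the first under Holm.

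**3. How often the readings differ, given that Family 2 is reached.** At 80% power and one-sided 0.008, each test statistic has mean about 2.41 + 0.84 = 3.25; 60% of that is 1.95. In simulations of three correlated normal statistics (1,000,000 draws per setting, equal effects, correlation 0 to 0.7), the decisions differed in 0.9 to 1.8% of trials at full effect and 2.1 to 3.1% at 60% of it. A separate run with means of 2.0 to 3.25 and correlation 0 or 0.5 gave 0.95 to 2.7%.

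**4. Allowing for the gate.** Family 2 opens only if both primaries and ECD superiority succeed. Assume that ECD is independent of IOP, and leave aside the further requirement on the primaries.

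- ECD difference 0%, as in Section 13.3.2: superiority succeeds about 2.5% of the time, so at most 0.025 × 3.1% = 0.08% of trials.
- ECD difference 4.393%, the 80%-power size in Section 13.3.4.2: 0.8 × 0.9% = 0.7% to 0.8 × 3.1% = 2.5% of trials.

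**5. Familywise error.** With all nulls true and independent tests, Holm gives 1 − (1 − 0.008333)³ = 0.02479. The listed steps add the cases with no p-value at or below 0.008333 but either two at or below 0.0125 or all three at or below 0.025. With a = 0.0125 − 0.008333 = 0.004167 and b = 0.025 − 0.0125 = 0.0125, the addition is 3a²(1 − 0.0125) + a³ + 3ab² + b³ = 0.00006, which gives 0.02485.

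With correlations of 0, 0.5, 0.8 and −0.49, and one, two or all three nulls true, the simulated maximum for the listed steps was 0.0252. Holm gave the same 0.0252 in that setting. The simulation standard error is √(0.025 × 0.975 / 1,000,000) = 0.00016.

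**6. Worst case over all dependence, all nulls true.** The listed steps reject if at least one p-value is ≤ α/3, two are ≤ α/2, or three are ≤ α. The largest attainable probability is 3(α/3)/1 + 3(α/2 − α/3)/2 + 3(α − α/2)/3 = α(1 + 1/4 + 1/2) = 1.75 × 0.025 = 0.04375. A linear program over all joint distributions gave the same value. Holm guarantees 0.025.

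**The case against.** The strongest reply is that the plan does commit to Holm. Section 13.5.3 names it before the list and again after it, Sections 13.2.2, 13.3.4 and 13.7.3 name it too, and the thresholds are exactly Holm's. A statistician told to apply Holm would stop at the first non-rejection. That stands: this is a correctly named method with an incomplete description. A reader might infer that the sponsor has adopted a different, more liberal procedure, but the documents do not support that. What remains is that the steps are introduced as the way Holm will be applied, and none of the other sections supplies the missing condition.

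A reader might also infer that type I error is inflated. That is not shown. The listed steps reject a subset of what Hochberg rejects at the same thresholds, so error is controlled under independence or the usual positive dependence. Positive dependence is the natural expectation here: all three endpoints are IOP measures in the same eye, and the spike endpoint (Section 13.1.1.1) is cumulative over visits that include 6 and 24 hours. The 0.04375 figure is a bound over every possible dependence, not an expected error rate.

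Finally, the 1 to 3% should not be read as a rate over all trials. It applies after a three-part gate and rests on assumed effects, whereas Section 13.3.1 expects the two OVDs to behave similarly. The opening of Section 13 also leaves further detail to a SAP approved before database lock. That is a suitable place for the clause, but no stop rule appears in the text available.

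**Conclusion.** The point holds as a minor one: the steps listed in Section 13.5.3 contradict the method the section names. Taken literally they can only add superiority claims, and those claims can be incoherent. Conditional on reaching Family 2, with all three IOP effects equal and at 60 to 100% of their 80%-power size, decisions differ in about 1 to 3% of simulated trials; unconditionally the figure is smaller. No familywise inflation above 0.025 was seen beyond simulation error. What is lost under the literal reading is Holm's control under arbitrary dependence. The primary tests, the ECD superiority test and trial success are untouched.

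**What to change.** In Section 13.5.3, add to steps 2 and 3: *only if the null hypothesis in the preceding step was rejected; otherwise testing stops and all remaining null hypotheses are retained*.

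Replace the tripled and doubled comparisons with adjusted p-values defined as the running maximum of (3p1, 2p2, p3), capped at 1, where p1 ≤ p2 ≤ p3. For the example above these are 0.030, 0.030 and 0.30, all above 0.025, so nothing is rejected, in agreement with Holm.

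The same wording should go into the SAP before database lock. Thresholds, sample size and power figures stay as they are. The only cost is the few extra claims that the literal text would allow.

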13.5.3.1 Secondary Safety Analyses

13.5.3.1.1 Incidence of $IOP \geq 30 \text{ mmHg}$

The null hypothesis of no difference between treatment groups in the proportion of subjects with $IOP \geq 30 \text{ mmHg}$ at any follow-up visit will be tested using a chi-square test for the Safety set. A two-sided 95% confidence interval will be constructed around the difference between groups using the normal approximation. If the null hypothesis is rejected then statistical superiority will be claimed for the test OVD in this endpoint.

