13.2.2.1 Secondary Safety Hypotheses

13.2.2.1.1 IOP Spike Rate Superiority Test

The secondary safety null hypothesis regarding the IOP spike rate is that the test incidence (π_t) of IOP observations at or above 30 mmHg is greater than or equal to the control incidence (π_c) of IOP observations at or above 30 mmHg. The alternative hypothesis is that the test incidence is less than the control incidence.

$$H_0: \pi_t \geq \pi_c$$

$$H_1: \pi_t < \pi_c$$

If the null hypothesis is rejected then superiority will be claimed for the test OVD in the rate of IOP spikes.

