13.5.3.2 Secondary Effectiveness Analysis

The null hypothesis of no difference between treatment groups in ECD loss will be tested for the ITT set using the multiple imputation method and statistical model described above for the primary effectiveness analysis. A two-sided 95% confidence interval will be constructed around the difference between groups. If the null hypothesis is rejected then statistical superiority will be claimed for the test OVD in this endpoint.

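### The analysis text for the spike-rate and ECD superiority tests states non-directional nulls and claims superiority on any rejection, in conflict with the one-sided hypotheses and power basis set elsewhere in the protocol

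*Combined protocol and SAP*

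**What the plan says.** **Hypotheses and levels.** Section 13.2.2 states that "the nominal alpha risk will be 0.025 for the one-sided secondary superiority hypothesis tests". For spikes, section 13.2.2.1.1 takes as null that the test incidence is at least the control incidence, and continues: "The alternative hypothesis is that the test incidence is less than the control incidence". The claim is tied to that null: "If the null hypothesis is rejected then superiority will be claimed for the test OVD in the rate of IOP spikes". Section 13.2.2.2 sets a directional null for ECD loss in the same way.

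**Power basis.** Section 13.3.4 bases its detectable effects on one-sided tests. Section 13.3.4.1.1 describes the spike test as a chi-square test at a one-sided level of 0.008 with 80% power for 0.117 against 0.256. Section 13.3.4.2 gives 80% power for an ECD difference of 4.393% at a one-sided level of 0.025. Both assume 165 per arm.

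**Analysis text.** Section 13.5.3.1.1 starts from "The null hypothesis of no difference between treatment groups in the proportion of subjects with" an IOP of 30 mmHg or more, says that this null "will be tested using a chi-square test for the Safety set", and ends: "If the null hypothesis is rejected then statistical superiority will be claimed for the test OVD in this endpoint". Section 13.5.3.2 reads "The null hypothesis of no difference between treatment groups in ECD loss will be tested for the ITT set", with the same unconditional claim.

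**Decision rule.** In section 13.5.3, "The smallest of the three raw p-values will be compared to 0.008333", and the later Holm steps use 0.0125 and 0.025. That section also says that p-values decide and confidence intervals do not. The three IOP tests open only after both primary endpoints and ECD superiority are met.

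**The concern.** A Pearson chi-square statistic is a squared quantity, so its ordinary p-value counts departures in both directions. Section 13.5.3.1.1 does not say how that p-value becomes one-sided, and its null has no direction. Two programmers could therefore work from the same protocol and reach different decisions. One would put the ordinary chi-square p-value into the Holm table. The other would follow sections 13.2.2.1.1 and 13.3.4.1.1 and halve it when the estimate favours the test OVD. At the first Holm step, a two-sided p between 0.008333 and 0.016667 fails on the first reading and passes on the second. For ECD the disputed interval is 0.025 to 0.05, and that test is the gate to every IOP superiority claim.

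The wording also omits any check of direction. The two-sided 95% intervals in both sections cannot supply one, because section 13.5.3 bars intervals from deciding.

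**Working it through.** **1. Spike test: reproduce the stated power.** Inputs from section 13.3.4.1.1: p1 = 0.117, p2 = 0.256, n = 165 per arm. Pooled-variance normal approximation, no continuity correction:

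power = Φ{[√n·|p1 − p2| − z·√(2·p̄·(1 − p̄))] / √(p1(1 − p1) + p2(1 − p2))}

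- p̄ = 0.1865
- √(2 × 0.1865 × 0.8135) = 0.5508
- √(0.117 × 0.883 + 0.256 × 0.744) = 0.5420
- √165 × 0.139 = 1.7855

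| p-value used | Threshold | Tail area | z | Power |
|---|---|---|---|---|
| One-sided | 0.008 | 0.008 | 2.409 | Φ(0.846) = 80.1% |
| One-sided | 0.008333 | 0.008333 | 2.394 | Φ(0.861) = 80.5% |
| Two-sided | 0.008333 | 0.004167 | 2.638 | Φ(0.613) = 73.0% |

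The stated 80% reproduces as one-sided. At the later Holm steps the one-sided and two-sided figures are 84.5% and 77.5% (0.0125), and 90.4% and 84.5% (0.025). With the two-sided p-value, 80% power at 0.008333 would need 189 per arm.

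**2. ECD test: reproduce the stated power.** Inputs from section 13.3.4.2: difference 4.393%, SD 14.2%, n = 165, 328 degrees of freedom.

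- Standard error = 14.2 × √(2/165) = 1.563
- Non-centrality = 4.393 / 1.563 = 2.810
- One-sided at 0.025: critical t = 1.967, power 80.0%
- Two-sided p against 0.025 (tail area 0.0125): critical t = 2.252, power 71.2%

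**3. Could a harmful spike difference be claimed as superiority?** It would first have to pass the primary non-inferiority test, with an upper limit below 0.117 (section 13.5.1). All outcome pairs with complete data were enumerated, using a one-sided 95% Wald limit and the two-sided chi-square p-value.

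- At 165 per arm, both conditions with the test arm worse require at most 4/165 (2.4%) observed control spikes at 0.008333, or 7/165 (4.2%) at 0.025.
- Example: 16/165 against 4/165. The difference is 0.0727 and its SE 0.0260. The upper limit is 0.0727 + 1.645 × 0.0260 = 0.115, and the chi-square p is 0.0056.
- At 184 per arm the limits are 6/184 (3.3%) and 9/184 (4.9%).

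Joint chance of passing non-inferiority with a significantly worse test arm, at 165 per arm and before the ECD gates:

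| True rates, test vs control | Threshold 0.008333 | Threshold 0.025 |
|---|---|---|
| 11.7% vs 11.7% (planning) | 1.1 × 10⁻⁶ | 7.1 × 10⁻⁵ |
| 18% vs 11.7% (assumed) | 1.5 × 10⁻⁸ | 2.6 × 10⁻⁶ |
| 8% vs 2% (assumed) | 21% | 37% |

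**4. The same question for ECD**, using an unadjusted t-test at 165 per arm and SD 14.2%.

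- A wrong-direction two-sided p at or below 0.025 needs an excess loss of at least 2.252 × 1.563 = 3.52%.
- Passing the 5% margin needs an excess below 5 − 1.650 × 1.563 = 2.42%. The two cannot both hold.
- They become compatible when the SE falls below 5 / (1.650 + 2.252) = 1.282, that is, an SD below 1.282 / √(2/165) = 11.6%. The same calculation at 184 per arm gives 12.3%.

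**The case against.** The strongest reply is that sidedness is already settled. Section 13.2.2 calls the secondary tests one-sided, section 13.2.2.1.1 gives a directional null for this endpoint, and section 13.3.4.1.1 names a chi-square test at a one-sided level. On that view the analysis section is loose shorthand, and the SAP can supply the p-value construction. The reply is right about intent. It does not remove the conflict: the analysis sections contain their own null and their own claim rule, and both differ from section 13.2.2.

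Three stronger readings are tempting, and the documents do not support them.

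- **A reader might infer that the 80% power figures are wrong.** They are not. Both reproduce under the one-sided tests that the protocol specifies, and the loss arises only if the analysis text is followed literally. The figures are also detectable effects for gated secondary tests; the sample size rests on the primary endpoints. A two-sided p against a one-sided threshold is conservative for a favourable claim, so it does not inflate false favourable claims.
- **A reader might infer that an excess of spikes on the test OVD would be reported as superiority.** The wording permits it, but the primary non-inferiority test blocks nearly all such cases at the planned 11.7% control rate, and the ECD gate lowers the chance further. It is not impossible, because section 13.3.1 cites published spike rates from 0.0% upward.
- **A reader might extend the power loss to the mean-IOP tests.** Section 13.5.3.1.2 contains no null of no difference. It refers to the null hypothesis, which section 13.2.2.1.2 defines directionally.

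**Conclusion.** The inconsistency stands for the spike-rate and ECD superiority tests. Their decision rule in section 13.5.3 does not match the hypotheses in section 13.2.2 or the power basis in section 13.3.4. Read literally, power is about 7 points lower for spikes (80.5% to 73.0%) and about 9 points lower for ECD (80.0% to 71.2%). Read with section 13.2.2, nothing is lost. The practical defect is that the protocol leaves room for both readings over an interval of p-values where they give opposite decisions.

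The wrong-direction risk is secondary. It depends on departures from planning: an observed control spike rate of about 2–4% or less at 165 per arm, or an ECD SD below about 12%.

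These results assume complete data, a normal approximation for proportions and an unadjusted t-test for ECD; the planned ECD model also includes investigator and multiple imputation. The spike check uses the one-sided 95% limit. Section 13.5.1 also mentions a two-sided 95% interval, whose upper limit would tighten the gate to 3/165 and 5/165 control spikes at the two thresholds.

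**What to change.** In sections 13.5.3.1.1 and 13.5.3.2, and in the SAP before unmasking:

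1. Replace the nulls of no difference with the directional nulls of sections 13.2.2.1.1 and 13.2.2.2.
2. Define the p-value as the one-sided probability, in the direction favouring the test OVD, of the signed statistic. For spikes this is the signed square root of the chi-square; for ECD loss it is the signed t from the combined imputation model.
3. Allow the superiority claim only when the estimate favours the test OVD and this one-sided p-value meets its threshold: the applicable Holm step for spikes, 0.025 for ECD loss.

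The cost is one or two sentences in each section. Data collection, sample size and the stated power figures stay as they are.

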13.5.3.1.2 Mean Change from Baseline in IOP

Change from baseline in IOP (mm Hg) will be computed as post-op IOP minus baseline IOP and will be summarized using continuous summary statistics for the Safety Population by scheduled Visit and actual treatment received in a table. A statistical model will be constructed by visit with change from baseline in IOP as the dependent variable, treatment group, investigator, as a fixed factor, baseline IOP as a continuous covariate, and subject as a random factor. For each study visit (6 hours post-op and 24 hours post-op), superiority will be claimed for the test OVD in this endpoint if the null hypothesis is rejected.

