7.1 Overall Study Design and Plan Description

This will be a multicenter, controlled, randomized, monocular trial of Bausch & Lomb DVisc40 (test) OVD compared to the currently marketed Alcon VISCOAT[®] (control) OVD.

Subjects scheduled to undergo cataract surgery by phacoemulsification and implantation of a posterior chamber intraocular lens (IOL) will be screened for eligibility. Subjects will be examined preoperatively to obtain a medical history, to establish a baseline for ocular condition, including ECD, and to determine eligibility. Only one eye of each subject will be included in the study. In the event that both eyes are eligible to participate in the study, the selection of the study eye will be left to the Investigator's discretion. At the time of surgery, subjects will be randomly assigned to either of the OVD groups based upon a predetermined randomization scheme. Randomization will be by a 1:1 schema (DVisc40:VISCOAT[®]) and will be stratified by site, age group and cataract severity. A method other than stratification may be employed to balance randomization. If so, the method will be specified in the statistical analysis plan (SAP).

Postoperatively, subjects will undergo ophthalmic examinations at regular intervals per the study visit schedule (refer to [Appendix A](#)). The Investigator will provide standardized pre-, intra-, and postoperative care for all study subjects at his/her site (refer to Section 11 for additional information). A delegated examiner at each site who is masked to the randomized assignment of each subject will perform all postoperative assessments.

The VISCOAT[®] OVD was chosen as the control because the product has been used in cataract surgery for over 20 years and has a proven record for safety. In addition, VISCOAT[®] OVD is classified as a dispersive OVD as is the DVisc40 OVD.

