9.3.4 Management of Raised IOP

Treatment for IOP < 30 mmHg should be avoided if possible unless the Investigator considers it necessary for the safety and well-being of the subject. In the case of treatment of IOP < 30 mmHg, a specific justification must be documented in the subject's source records and on the case report form. Use of an IOP lowering agent under these conditions is not a reason for discontinuing a subject from the study. However, they are to be excluded from the Per Protocol (PP) and Best Case analysis populations.

For any IOP measurement ≥ 30 mmHg at a study visit (or as determined as medically necessary by the Investigator), the Investigator should institute a treatment consisting of one or a combination of the following options:

- Aqueous fluid release through corneal incision;
- Topical eye drops (e.g., *B*-blocker, prostamide, etc.);
- Oral medication (e.g., acetazolamide).

An IOP ≥ 30 mmHg at a study visit must be rechecked in approximately one (1) hour after the initial IOP measurement.

In the event of an IOP \geq 30 mmHg or the use of an IOP lowering treatment, the Investigator should contact the Sponsor and its representative immediately.

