11.1.4 Unscheduled Visit(s)

Additional visits may be scheduled, as necessary, to ensure the safety and well-being of subjects. In cases where the subject's IOP is ≥ 30 mmHg, additional Unscheduled Visits may be scheduled as necessary to monitor the subject's IOP (see Section 11). All additional examinations should be fully documented in the site source documents and on Unscheduled Visit CRFs, as appropriate. Visits intended to fulfill scheduled visit requirements that fall outside the designated scheduled visit range, are not Unscheduled Visits. In these cases, the visit data will be collected and transcribed to the appropriate scheduled visit CRF.

If a subject is seen for multiple visits during a given visit timeframe, the data from the visit that is intended to meet the protocol requirements for the scheduled visit should be captured on the corresponding visit CRF. Where such a determination cannot be made, the first visit within the scheduled visit interval will be used for completion of the protocol required scheduled visit CRF. Data from any additional visits within a scheduled visit interval will be captured on an Unscheduled Visit CRF.

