13.3.4.1.2 Mean Change from Baseline in IOP

A sample size of 165 in each group will have 80% power to detect a difference in means of 1.797 mm Hg assuming that the common standard deviation is 5.0 mm Hg using a two-group t-test with a 0.008 one-sided significance level.

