13.5.1 Primary Safety Analysis

IOP will be assessed in the study eye using Goldmann tonometry at each scheduled follow-up visit and may be assessed at unscheduled visits.

Subjects with $IOP \geq 30$ mmHg at any follow-up visit ($IOP \geq 30$ mmHg at any follow-up visit, No $IOP \geq 30$ mmHg at any follow-up visit) will be summarized using categorical summary statistics for the Safety Population by actual treatment received in a table. Missing data will not be imputed for this summary table.

Missing IOP values will be imputed using Markov chain Monte Carlo (MCMC) methods. Twenty imputed datasets will be produced using a seed of 1017144149. The variables used in the imputation model will include IOP at baseline and at each of the scheduled postoperative visits. After missing data at scheduled visits has been imputed, unscheduled visit IOP values will be added to each imputed dataset.

Within each imputed dataset, subjects will be classified as belonging to one of the following groups:

- $IOP \geq 30$ mmHg at any follow-up visit
- No $IOP \geq 30$ mmHg at any follow-up visit

This classification will be based on experiencing at least one IOP measurement of 30 mmHg or more at any follow up visit over the entire course of the study. Subjects experiencing one or more IOP spikes will be counted only once.

The difference between test and control in the proportion of subjects with $IOP \geq 30$ mmHg at any follow-up visit and the asymptotic standard error will be estimated separately for each imputation.

An estimated difference between treatment groups and a two-sided asymptotic Wald 95% confidence interval around the difference will be constructed via combination of the proportion differences and standard errors from the imputations. If all the imputations result in the same estimated difference and confidence interval, then the results of a single imputation may be used.

If the upper confidence limit (equivalent to a one-sided upper 95% confidence limit) is less than 0.117 (11.7%), then the null hypothesis of inferiority will be rejected in favor of the alternative hypothesis of non-inferiority. A p-value will also be provided for this one-sided hypothesis test.

The primary safety analysis will be repeated using the Per Protocol Population as a sensitivity analysis with observed data only (i.e. without imputation).

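### The by-visit IOP-change model has a random subject effect that one value per subject cannot separate from residual error

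*Combined protocol and SAP*

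**What the plan says.** Section 13.5.3.1.2 states: "A statistical model will be constructed by visit with change from baseline in IOP as the dependent variable". The explanatory terms are treatment group, investigator (fixed), "baseline IOP as a continuous covariate, and subject as a random factor". No visit term, treatment-by-visit term, within-subject covariance or degrees-of-freedom method is given. Superiority may be claimed separately at 6 hours and at 24 hours.

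The data feeding each model are set elsewhere:

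- Section 7.1: "Only one eye of each subject will be included in the study".
- Section 13.5.1: "IOP will be assessed in the study eye using Goldmann tonometry at each scheduled follow-up visit". Appendix B, item 4.0, asks for no replicate IOP readings, whereas items 3.0 and 6.0 ask for three ECD images and three pachymetry readings.
- Section 11.1.4: "Data from any additional visits within a scheduled visit interval will be captured on an Unscheduled Visit CRF", so extra visits do not add to the scheduled-visit record.
- Section 9.3.4: an IOP of 30 mmHg or more "must be rechecked in approximately one (1) hour after the initial IOP measurement". Nothing places that recheck in this model.

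Section 13.3.4.1.2 sizes the endpoint with a plain two-group t-test: "A sample size of 165 in each group will have 80% power to detect a difference in means of 1.797 mm Hg", given that the "common standard deviation is 5.0 mm Hg using a two-group t-test with a 0.008 one-sided significance level".

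**The concern.** A random subject effect needs at least some subjects with more than one observation. In a model fitted by visit here, the subject factor has as many levels as there are observations, so subject variation and residual variation are the same quantity under two names.

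Two of the three Family 2 tests rest on this model. Section 13.5.3 says that rejection depends on the p-values and the Holm adjustment, not on the confidence intervals. The standard error and the reference distribution therefore decide the claim. If the model is run as written, both can depend on which software, optimiser and df method the programmer happens to use.

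**Working it through.** **1. The plan's own figure.** Inputs from 13.3.4.1.2: n = 165 per group, SD 5.0, one-sided alpha 0.008, power 80%. The standard error of the difference is 5.0 × √(2/165) = 0.5505. Solving the noncentral t power equation with 2 × 165 − 2 = 328 df gives a detectable difference of 1.7973 mm Hg. Power at 1.797 is 79.98%. The stated 1.797 reproduces, and its calculation contains no subject effect.

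**2. Identifiability.** Let X hold the fixed terms and Z the subject indicators. With one record per subject, Z = I, so

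V = σ²(subject) × ZZ′ + σ²(residual) × I = [σ²(subject) + σ²(residual)] × I.

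Only the sum enters the likelihood. In a simulated dataset (N = 330, 18 sites, assumed balanced with no missing visits), the REML log-likelihood was −957.209 whether 0%, 25%, 50%, 75% or 99% of the variance was assigned to subject.

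**3. Degrees of freedom.** With 18 investigator levels (section 7.2 gives up to about 18 sites):

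- rank(X) = 1 intercept + 1 treatment + 1 baseline IOP + 17 investigator = 20.
- N − rank(X) = 330 − 20 = 310. This is the error df for the treatment test.
- rank([X Z]) = 330, so N − rank([X Z]) = 0. This counts df for a residual separate from subject.

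| N | Sites | rank(X) | N − rank(X) | N − rank([X Z]) |
|---|---|---|---|---|
| 330 | 18 | 20 | 310 | 0 |
| 368 | 18 | 20 | 348 | 0 |
| 330 | 10 | 12 | 318 | 0 |
| 330 | 6 | 8 | 322 | 0 |

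**4. What a fit returns.** On the same simulated data, least squares without the subject term gave a treatment estimate of −1.511, SE 0.527 and residual variance 22.84. A REML mixed model with the term gave:

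- the same estimate, −1.511;
- a variance split of 11.42 and 11.42, whose sum of 22.84 matches least squares;
- SE 0.488, with a warning that the Hessian was not positive definite, although convergence was reported.

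The ratio is 0.488/0.527 = 0.93. In another simulated dataset, two optimisers split the variance as 12.6/12.6 and 1.8/23.4. Both sum to 25.2, and there the SE equalled least squares.

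Over 100 simulated datasets in one package, the estimate always equalled least squares and convergence was always reported. The median SE ratio was 0.9997. In the worst 5% of fits the SE was at least 6% too small, with a minimum ratio of 0.43, and it was never materially too large. As an illustration, a ratio of 0.93 would turn the first Holm threshold of 0.00833 into about 0.013.

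**5. Without the term.** ANCOVA with 310 df and SD held at 5.0 has a detectable difference of 1.798 mm Hg and power of 79.96% at 1.797. Simulated one-sided type I error at nominal 0.025 was 0.0251 (20,000 runs).

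**The case against.** The strongest reply is that the term is redundant but harmless. The treatment contrast and total variance are estimable, the point estimate equals least squares, and the SE is usually right. Even a normal reference in place of 310 df moves the critical value at 0.00833 only from 2.407 to 2.394. Most of this stands. What remains is that some fits returned too small an SE, always with convergence reported, and that no df method is specified.

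A second reply is that a single repeated-measures model reported by visit was meant, where a subject effect belongs. The text does not support this: it lists no visit or treatment-by-visit term, so such a model could not deliver the separate 6-hour and 24-hour tests in 13.2.2.1.2. The sentence needs correcting on either reading.

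A third reply is that these tests matter little. They are reached only if both primaries and ECD superiority succeed. Under the planning assumption of a 0% ECD difference (13.3.2), the Family 1 test at one-sided 0.025 would succeed at most about 2.5% of the time. That is fair and limits the weight of the point, but each test still supports a superiority claim if reached.

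A reader might infer more: that the model leaves no error df at all, cannot be estimated, yields no valid p-value, or forces a model change after unmasking. The documents do not support this. Zero df applies only to a residual separate from subject; whether software uses that as its denominator depends on a df method the plan does not name, and no fit examined returned zero df or was refused. Section 13 leaves further detail to a SAP approved before database lock, so the correction can be made in time.

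**Conclusion.** The model is wrong as written, with limited consequences. The subject variance cannot be separated from residual error in a by-visit model with one eye and one scheduled value per subject. The treatment test itself survives, with about 310 df at 330 subjects and 18 sites. The exposure is software-dependent standard errors or df for two claim-bearing Family 2 p-values; where the SE was wrong in the fits above, it was too small.

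Both primary endpoints, the sample size and the stated 1.797 mm Hg are unaffected.

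The identifiability result follows from the design and needs no simulation. The df figures assume one investigator level per site and no missing visits. The size of the SE error rests on simulated data and will differ between programs. The conclusion also assumes that the one-hour recheck does not enter as a second record, since nothing in the plan says that it does.

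**What to change.** Before database lock, choose one of the following and write it into 13.5.3.1.2 and the SAP:

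- **Separate models (simplest).** Delete the random subject factor. At each of 6 and 24 hours fit an ANCOVA of IOP change on treatment, investigator and baseline IOP, with one value per subject per visit.
- **Joint model, if that was intended.** Fit one repeated-measures model to the 6-hour and 24-hour changes with treatment, visit, treatment-by-visit, investigator, baseline IOP and an unstructured within-subject covariance. Test the treatment contrast at each visit and name the df method.

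The first option costs one sentence. The detectable difference moves from 1.797 to 1.798 mm Hg, and neither the sample size nor the Holm procedure changes. The second takes a slightly longer specification.
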